## 14.5 Missing Date of Investigational Product

When the date of the last dose of investigational product is missing for a subject in the Safety Analysis Set, all efforts should be made to obtain the date from the investigator. If it is still missing after all efforts, then the last visit date when investigational product was returned will be used in the calculation of treatment duration.

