## 8. EXTENT OF EXPOSURE AND TREATMENT COMPLIANCE

## 8.1 Exposure to Investigational product

Exposure to double-blind investigational product for the Safety Analysis Set will be summarized with descriptive statistics (n, mean, SD, minimum, median, and maximum) and presented by treatment group. Exposure and compliance to investigational product will be listed for the Safety Analysis Set. The following will be calculated for the investigational product:

- Treatment duration, which is calculated as the number of days from the date of first dose of double-blind investigational product taken to the date of the last dose of double-blind investigational product taken, inclusively. Investigators are allowed to interrupt the study treatment to allow adverse events to resolve, if necessary. Any drug interruption will be subtracted off the treatment duration above to get the final treatment duration. Treatment duration will be presented as the number of weeks in the summary tables.
- Total dose, which is calculated as (total dispensed total returned) \* xxmg.
- The average daily dose will be calculated as total dose from above / duration of study drug exposure in days.

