## **8.2** Measurement of Treatment Compliance

Investigational product dosing compliance for a specified period is defined as the total number of capsules actually taken by a subject during that period divided by the number of capsules expected to be taken during the same period multiplied by 100. The total number of capsules actually taken is calculated by the total number of capsules dispensed minus the number of capsules returned. If a blister pack is not returned, the number of capsules returned for that blister pack will be imputed to zero. The number of capsules expected to be taken is calculated as the number of days that subject was in the particular period multiplied by the number of capsules to be taken per day during that period. The investigational treatment compliance over the entire study will be therefore calculated using the formula:  $100 \times [(total)]$ 

number of capsules dispensed) – (total number of capsules returned)]/ (total number of capsules planned to be taken per day  $\times$  duration of study drug exposure in days). The investigational treatment compliance will be categorized as < 80, 80-120, and > 120% and the number and percentage of patients in the Safety Analysis Set will be presented by treatment group.

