## 14.6.2 Incomplete Stop Date

The following rules will be applied to impute the missing numerical fields. If the date of the last dose of investigational product is missing, then replace it with the last visit date. If the imputed stop date is before the start date (imputed or non-imputed start date), then the imputed stop date will be equal to the start date.

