## 15. APPENDIX

Appendix 1: Classification of Visits Window

Timing of assessment (days relative to Treatment a)	Visit	Visit Name to display for Analysis
<=-1 Day	Screening	Visit 1 (Screening)
Visit 2 (Week 0 [Day 1])	Baseline	Visit 2 (Baseline)
Week 2, Day 14 (2-22 Days)	Visit 3	Visit 3 (Week 2)
Week 4, Day 28 (23-43 Days)	Visit 4	Visit 4 (Week 4)
Week 8, Day 56 (44-71 Days)	Visit 5	Visit 5 (Week 8)
Week 12, Day 84 (72-127 Days)	Visit 6	Visit 6 (Week 12)
Week 24, Day 168 (128-211 Days)	Visit 7	Visit 7 (Week 24)
Week 36, Day 252 (212-295 Days)	Visit 8	Visit 8 (Week 36)
Week 48, Day 336 (296 Days-End of Study)	Visit 9- End of Treatment	Visit 9 (Week 48)
Week 52, 4 weeks after completion of dosing (>End of Study)	Visit 10-Follow-up	Visit 10 (Week 52)

\* For early termination patients, MRI and liver biopsy visits happened after early termination date will be mapped to same visit as the early termination visit, even though the visit date is later than End of Study date.

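### When the last-dose date is imputed, a supply issued at the last return visit counts as taken although its days lie outside treatment duration

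*SAP*

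**What the plan says.** Four provisions of the SAP meet here.

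- **Section 8.1, duration.** Treatment duration runs from the first dose "to the date of the last dose of double-blind investigational product taken, inclusively", less any interruptions.
- **Section 14.5, missing last-dose date.** If the date is still missing after efforts to obtain it from the investigator, "then the last visit date when investigational product was returned will be used in the calculation of treatment duration".
- **Section 8.2, capsules taken.** "The total number of capsules actually taken is calculated by the total number of capsules dispensed minus the number of capsules returned". For missing packs: "If a blister pack is not returned, the number of capsules returned for that blister pack will be imputed to zero". Whole-study compliance divides this count by planned capsules per day times the duration of exposure, and is reported by treatment group as <80, 80-120 and >120%.
- **Section 8.1, dose.** Total dose is likewise built from dispensed and returned product. "The average daily dose will be calculated as total dose from above / duration of study drug exposure in days".

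Section 8.2 opens by defining compliance for a specified period, with capsules taken and capsules expected both referring to that one period. The whole-study formula that follows does not repeat this condition.

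**The concern.** Take a subject who hands in used packs at a clinic visit, receives the next supply there, and is not seen again. If the last-dose date cannot be obtained, Section 14.5 stops the day count at that visit. The new supply is never returned, so Section 8.2 counts every capsule in it as taken. The numerator then covers an interval that the denominator leaves out, and nothing else in the SAP removes that supply from the dispensed count or adds its days to the duration.

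The result does not depend on what the subject did afterwards. Someone who took none of the last supply gets the same inflated compliance as someone who took all of it. Average daily dose is inflated by the same factor and can exceed the planned daily dose purely through the rules. These quantities are only described, but the SAP supports an abbreviated report whose content is largely descriptive safety and exposure, so they should be right as far as the data allow.

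**Working it through.** The SAP states no compliance figure to reproduce. The check applies its own formula to the subject described above.

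**Inputs from the SAP**
- Compliance = 100 × (dispensed − returned) / (capsules per day × exposure days), Section 8.2.
- Exposure days end at the last return visit, day D, Section 14.5.
- A pack issued at D and not returned has returned = 0, Section 8.2.
- Target days 14, 28, 56, 84, 168, 252 and 336, Appendix 1.

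**Assumptions not in the SAP**
- Each visit issues exactly enough product to reach the next target day N, so the last supply covers S = N − D days.
- There are no interruptions.
- Adherence a before D is 100% or 80%.
- Treatment duration and duration of study drug exposure are the same quantity. The SAP uses both terms and defines no second duration.

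**Formula.** Capsules per day cancel, so compliance = (a × D + S) / D = a + S/D. Average daily dose, as a multiple of the planned daily dose, is the same expression.

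| D | N | S | a = 100% | a = 80% |
|---|---|---|---|---|
| 14 | 28 | 14 | 28/14 = 200% | 25.2/14 = 180% |
| 28 | 56 | 28 | 56/28 = 200% | 50.4/28 = 180% |
| 56 | 84 | 28 | 84/56 = 150% | 72.8/56 = 130% |
| 84 | 168 | 84 | 168/84 = 200% | 151.2/84 = 180% |
| 168 | 252 | 84 | 252/168 = 150% | 218.4/168 = 130% |
| 252 | 336 | 84 | 336/252 = 133.3% | 285.6/252 = 113.3% |

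Eleven of the 12 cases fall in the >120% category. Average daily dose is 1.13 to 2.00 times the planned daily dose.

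**Threshold.** Compliance passes 120% when S/D > 1.20 − a, that is S > 0.2 × D at full prior adherence and S > 0.4 × D at 80%. At Day 84 this means more than 16.8 or 33.6 days of supply. At Day 252 with 80% adherence it would need more than 100.8 days; the assumed supply is 84, so that case stays within 80-120%.

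**With matched periods.**
- Last supply left out of the numerator: a × D / D = a, so 100% or 80%, the assumed adherence.
- Last supply and its interval counted in both: (a × D + S) / (D + S), which is 100% at full adherence and 85.0–90.0% at 80%.

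Every matched result lies in the 80-120% category.

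**The case against.** The strongest reply is that the excess capsules come from the returned = 0 rule in Section 8.2, not from Section 14.5. Under the same assumptions, a subject resupplied at Day 84 who keeps the pack and has a known last dose on Day 85 computes to 168/85 = 198%. With a known last dose on Day 126 it is 168/126 = 133%. No imputed date is involved. This stands: the inflation is wider than the missing-date case, and the repair belongs mainly in Section 8.2. It does not remove the point, because in the missing-date case the imputed date excludes the whole interval of a supply that is counted in full.

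It is also fair to say that ending exposure at the last return visit is defensible, since accountability gives no evidence of intake after it. A reader might infer that the imputed duration is too short. The SAP does not support that, because the true last dose is unknown. The point is only that capsules and days must cover the same period.

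The SAP gives no dispensing schedule; Appendix 1 sets analysis windows. The percentages are therefore illustrations, and only the upward direction follows from the text.

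Finally, the consequence is limited. Compliance and average daily dose define no analysis set, Section 10 plans no inferential safety analysis, and values above 120% would be visible in their own category. All of that stands and limits the weight of the point.

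**Conclusion.** The point holds in a narrow form. For a subject whose last-dose date stays missing and whose last return visit included a resupply never returned, Sections 14.5, 8.1 and 8.2 together give an average daily dose and a whole-study compliance that are biased upward, contrary to the one-period principle in Section 8.2. If supplies last to the next Appendix 1 target day, compliance is about 133–200% with full prior adherence and 113–180% with 80%.

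Two further inferences are not supported. One is that every such subject is reported as over-compliant: the Week 36 case at 80% prior adherence gives 113%. The other is that the comparison between arms is biased: the SAP gives neither the number of affected subjects nor losses by arm. Only descriptive exposure and compliance summaries are affected.

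This is separate from the different fallback in Section 14.6.2 for medication and adverse event stop dates: "If the date of the last dose of investigational product is missing, then replace it with the last visit date". Aligning the two fallbacks would not cure the mismatch when the last visit is also the last return visit.

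**What to change.** In Section 8.2, cross-referenced from Sections 14.5 and 8.1, state that when the last-dose date is imputed by the last return visit, total dose, average daily dose and compliance use only product dispensed before that date minus product returned by that date. Flag these subjects in Listing 5.1 and footnote their number under Table 2.1.1.

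The cost is one sentence, two cross-references and a small change to the accountability program. The downside is that capsules truly taken from the last supply are not counted for these subjects, and the imputed duration itself does not change. The sentence also leaves untouched the related inflation for subjects with a known last-dose date and an unreturned pack, which comes from the returned = 0 rule and would need its own decision.

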## 14.6 Missing Date Information for Prior or Concomitant Medications

For prior or concomitant medications, including rescue medications, incomplete (i.e., partially missing) start date and/or stop date will be imputed. When the start date and the stop date are both incomplete for a subject, impute the start date first.

## 14.6.1 Incomplete Start Date

The following rules will be applied to impute the missing numerical fields. If the stop date is complete and the imputed start date is after the stop date, then the start date will be imputed using the stop date.

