## Missing day and month

- If the year of the incomplete start date is the same as the year of the date of the first dose of investigational product, then the day and month of the date of the first dose of investigational product will be assigned to the missing fields
- If the year of the incomplete start date is before the year of the date of the first dose of investigational product, then December 31 will be assigned to the missing fields
- If the year of the incomplete start date is after the year of the date of the first dose of investigational product, then 01 January will be assigned to the missing fields.

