#### Missing month only

• The day will be treated as missing and both month and day will be replaced.

- If the year of the incomplete start date is the same as the year of the date of the first dose of investigational product, then the day and month of the date of the first dose of investigational product will be assigned to the missing fields
- If the year of the incomplete start date is before the year of the date of the first dose of investigational product, then December 31 will be assigned to the missing fields
- If the year of the incomplete start date is after the year of the date of the first dose of investigational product, then 01 January will be assigned to the missing fields.

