#### Missing day only

- If the month and year of the incomplete start date are the same as the month and year of the date of the first dose of investigational product, then the day of the date of the first dose of investigational product will be assigned to the missing day
- If either the year is before the year of the date of the first dose of investigational product or if both years are the same but the month is before the month of the date of the first dose of investigational product, then the last day of the month will be assigned to the missing day
- If either the year is after the year of the date of the first dose of investigational product or if both years are the same but the month is after the month of the date of the first dose of investigational product, then the first day of the month will be assigned to the missing day.

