## 14.7 Missing Date Information for Adverse Events

For AEs, the default is to only impute incomplete (i.e., partially missing) start dates. Incomplete stop dates may also be imputed when calculation of the duration of an AE is required per the protocol. If imputation of an incomplete stop date is required, and both the start date and the stop date are incomplete for a subject, impute the start date first.

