## 14.7.1 Incomplete Start Date

Follow same rules as in Section 14.6.1.

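### When a start date in the first-dose year lacks its month, Section 14.6.1 moves the item to first-dose day even if its partial stop date falls in an earlier month

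*SAP*

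**What the plan says.** Section 14.6.1 handles incomplete start dates. With day and month missing and the year equal to the first-dose year, "then the day and month of the date of the first dose of investigational product will be assigned to the missing fields". If only the month is missing, the recorded day is discarded: "The day will be treated as missing and both month and day will be replaced", and the same rule follows. If only the day is missing and the recorded month is before the first-dose month, "then the last day of the month will be assigned to the missing day", so the item stays before treatment.

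The cross-check on an imputed start puts the recorded stop in its place, but only conditionally: "If the stop date is complete and the imputed start date is after the stop date, then the start date will be imputed using the" […]. Section 14.6 has the start imputed ahead of the stop when both are incomplete. Section 14.6.2 then settles any conflict in favour of the start, to which the stop is moved: "If the imputed stop date is before the start date (imputed or non-imputed start date), then the imputed stop date will be equal to the" […].

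Section 14.7.1 carries the start rule to adverse events: "Follow same rules as in Section 14.6.1". Section 14.7.2 does the same for stop dates, but stop imputation is optional there: "For AEs, the default is to only impute incomplete (i.e., partially missing) start dates".

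**The concern.** Giving an unknown onset the first-dose date is a normal conservative convention while the record leaves on-treatment onset possible. It goes wrong when the record rules that out. A stop date of known month and year, earlier than the first-dose month, shows that the item ended before treatment. The SAP uses such evidence when the stop is complete and ignores it when only the stop day is missing.

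At stake is TEAE status. Section 10.1 defines a TEAE partly by a start on or after first dose, so a moved event could enter the TEAE tables. If it is diarrhoea, it could also enter the onset-day summary. Where the stop is imputed to obtain a duration, onset and stop would both fall on first-dose day. If severity or relationship is missing, Sections 14.8 and 14.9 assign Severe (instead of Mild) and Related, because the imputed start is no longer before first dose.

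For medications, an item that ended before dosing would be labelled concomitant under Section 9.

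**Working it through.** The SAP states no figure on this point, so there is none to reproduce. The check applies the rules of Sections 14.6, 14.6.1 and 14.6.2 literally to example records.

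Assumed dates, for illustration only: first dose 15 Jun 2017, last dose 16 May 2018.

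**Affected record: start year 2017 only, stop Mar 2017 with the day missing**

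1. Start first (14.6). The month is missing and the year equals the first-dose year, so start = 15 Jun 2017.
2. Cross-check (14.6.1). The stop is not complete, so the check does not apply and the start stays at 15 Jun 2017.
3. Stop (14.6.2). The recorded year precedes the last-dose year, so the last day of the month is used: 31 Mar 2017.
4. Conflict rule (14.6.2). 31 Mar 2017 is before 15 Jun 2017, so stop = 15 Jun 2017.

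The latest stop the record allows is 31 Mar 2017. The analysis date is 30 + 31 + 15 = 76 days later. For an adverse event whose stop is not imputed, steps 3 and 4 drop out and the start remains at 15 Jun 2017 unchecked.

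**Comparison with neighbouring records**

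| Recorded start | Recorded stop | Start used | Stop used | Placed |
|---|---|---|---|---|
| 2017 only | Mar 2017 | 15 Jun 2017 | 15 Jun 2017 | on first-dose day |
| 2017, day 10, no month | Mar 2017 | 15 Jun 2017 | 15 Jun 2017 | on first-dose day |
| 2017 only | 20 Mar 2017 | 20 Mar 2017 | 20 Mar 2017 | before first dose |
| Feb 2017 | Mar 2017 | 28 Feb 2017 | 31 Mar 2017 | before first dose |
| 2016 only | Mar 2017 | 31 Dec 2016 | 31 Mar 2017 | before first dose |

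Rows 1 and 3 differ only in whether the stop day was recorded, which has no bearing on whether the item was over by 15 June. Rows 4 and 5 mark the limits of the problem.

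**Conditions that must all hold**

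- The start month is missing, with or without the day.
- The start year is the first-dose year.
- The stop is partial, with a recorded month before the first-dose month.

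**With the start capped at the latest date the partial stop allows**

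Row 1 becomes start = min(15 Jun 2017, 31 Mar 2017) = 31 Mar 2017 and stop = 31 Mar 2017, before treatment. For a medication this is also outside the 30-day window for prior use in Section 9 (76 > 30), so it would be neither prior nor concomitant.

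**The case against.** The strongest reply is that little depends on this. Section 1 says the study was terminated and the SAP serves an abbreviated report. Section 10 plans no inferential safety analysis. The error is conservative, since it adds TEAEs, and the rule is the same in every treatment group. An affected event also needs an unusual record, with a known end month but an unknown start month. All of this stands and limits the weight of the point. It does not justify a rule that overrides recorded information, and the SAP's own check against a complete stop shows that stop-date evidence was meant to prevail.

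Four stronger readings are tempting, and the SAP does not support them:

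- *Any item with partial dates that ended before first dose is moved.* It is not. A start missing only its day, a start in an earlier year, or a complete stop each keeps the item before treatment.
- *Every case is affected.* Listing each first-dose month with each earlier stop month in one year gives 0 + 1 + ... + 11 = 66 pairs, and all 66 are moved. That follows by construction, because only records meeting the conditions were listed. It says nothing about frequency.
- *Misclassification as a TEAE is certain.* Section 10.1 also requires the event to occur in the double-blind or follow-up phase. An event recorded as over before first dose arguably fails that condition. A program that tests only the imputed start would probably still flag it, so the risk remains.
- *A therapy stopped in screening would look like prohibited on-study use.* Section 6 describes a blinded review of the database and does not say that it uses imputed dates. A reviewer could see the recorded stop month.

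The medication side is also slight. Section 9 plans listings only, and Section 17.1 has no concomitant-medication table. Section 14.6 names medications, so applying it to non-drug therapies is by extension.

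**Conclusion.** The point holds within the three conditions above. The start rule, the limited cross-check, the start-first order and the stop rule together replace a recorded pre-treatment stop month with first-dose day, and no other section prevents it. This is a rule that gives a wrong result, not a missing detail.

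Its reach is small. For adverse events it means possible over-counting in descriptive TEAE tables and the diarrhoea onset summary, with Severe or Related added where those fields are blank. For medications it means a label in a listing. The SAP gives no count of affected records. That the number is small is a judgement based on how unusual the pattern is. The TEAE consequence assumes that programming relies on the imputed start date and does not separately exclude events recorded as ending before first dose.

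**What to change.** In Section 14.6.1, and so through 14.7.1 for adverse events, replace the cross-check with: *where the imputed start falls after the stop date, or after the latest date consistent with a partial stop date, set the start to that date.* In Section 14.6.2 add: *an imputed stop is never moved past its recorded month or year.*

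The conservative default survives wherever the record leaves on-treatment onset possible. If the stop is wholly missing, there is nothing to cap against. If it gives only the first-dose year, or the first-dose month, the latest consistent date is not before first dose and the start stays on first-dose day.

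The cost is one sentence in each of two sections and a small programming change. No new data are needed.

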## Missing day and month

- If the year of the incomplete start date is the same as the year of the date of the first dose of investigational product, then the day and month of the date of the first dose of investigational product will be assigned to the missing fields
- If the year of the incomplete start date is before the year of the date of the first dose of investigational product, then December 31 will be assigned to the missing fields
- If the year of the incomplete start date is after the year of the date of the first dose of investigational product, then 01 January will be assigned to the missing fields.

